4. HYPOTHESES AND DECISION RULES

4.1. Statistical Hypotheses

No statistical hypotheses will be tested in this study.

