8.3.4. Adverse Events

Adverse events will be reported in accordance with the sponsor reporting standards. Several minor ad-hoc adjustments and additions will be conducted.

In the case report forms (CRF) the infusion-related adverse effect was characterized by toxicity grade, instead of the conventional characterization of the AE by severity. The possible toxicity grades are 0,1,2,3,4. The values of toxicity grades = 0, 1, 2 will be mapped to the “mild” category of the AE severity score and values of the toxicity score equal to 3 and 4 will be mapped to the “moderate” and “severe” scores accordingly. The explanation of this mapping from toxicity to severity scale needs to be included into the footnote of the otherwise standard summaries of the adverse events.

Listings with the descriptions of infusion-related reactions (IRR) and injection site reactions (ISR) will be created (separately for all causalities and treatment related adverse events) with the description of individual adverse effects.

Similar listings describing subsets of all events of participants who had preferred term of a special interest that may suggest the occurrence of cytokine release syndrome, with start on Day 1-3 after dose 1 (IV or SC) or Day 1- 4 after dose 2 (SC) will be created (separately for all causalities and treatment related adverse events). The set of preferred term of interest will include tachycardia, hypotension, hypertension, chills, vomiting, nausea, headache, pyrexia, dizziness, and palpitations. The observation of a group of two or more events from this set within a short time window after the dosing will be viewed as a potential cytokine release syndrome event (PCRE). The tabulation showing total number of participants and number and percent of PCREs within each of the doses will be created. Note that this analysis is exploratory and the list of preferred terms may be modified if needed.

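### SAP 8.3.4 searches for possible cytokine-release events over three days after dose 1 but four after dose 2, without a reason, and these are the only windows available to define such an event.

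*SAP*

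**What the plan says.** SAP 8.3.4 names ten preferred terms that may suggest cytokine release, among them headache, nausea, dizziness and hypertension. It lists events from this set "with start on Day 1-3 after dose 1 (IV or SC"), and over Day 1 to Day 4 after dose 2, which is SC. No reason is given for the fourth day after dose 2. Route does not supply one, because dose 1 in Part B is also planned as SC and falls under the three-day window.

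The flag itself, the PCRE, is defined separately as "a group of two or more events from this set within a short time window after the dosing", and the length of that window is not stated. The summary table is to show "number and percent of PCREs within each of the doses will be created". The SAP does not say whether this means dose number (first or second) or dose level (mg).

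The SAP adds that "this analysis is exploratory and the list of preferred terms may be modified if needed". SAP 4.1 states: "No statistical hypotheses will be tested in this study". Under SAP 2.1, Part B participants are dosed on Day 1 and Day 29, and Part A participants once.

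**The concern.** The listed terms are common and non-specific, so some pairs will fall together by chance. Because a PCRE needs two events, the chance of a false flag grows faster than the length of the window: at low rates, roughly with its square. A window one day longer after dose 2 therefore adds flags that have nothing to do with the drug.

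Safety of single and multiple doses is the primary objective. Protocol 1.2.6 reports cytokine release in an in vitro human assay, and Protocol 1.6 expects infusion and injection reactions that may be severe. Readers of the Part B results will want to know whether reactions ease or worsen on re-dosing, even though no formal contrast is planned. An exploratory label does not correct a descriptive table whose rows rest on different search times.

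**Working it through.** **Inputs from the documents.** Search windows of 3 days after dose 1 and 4 days after dose 2 (SAP 8.3.4). At least two listed events for a PCRE (SAP 8.3.4). Part B cohorts B1 to B5, each with 6 active and 2 placebo (SAP Table 1): 5 × 6 = 30 active and 5 × 2 = 10 placebo. The plan gives no rate, power or error figure for this analysis, so there is none to reproduce.

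**Assumptions.** The listing windows also define a PCRE. Day 1 after dose 2 is the dosing day. Listed terms arise at a constant background rate r per participant-day, independently, and are recorded equally after both doses. The documents give no value for r, so a range of 0.01 to 0.20 is shown.

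**Reading 1: rows by dose number.** The chance of two or more background events in d days is P(d) = 1 − exp(−rd)(1 + rd). For r = 0.05:
- d = 3: 1 − exp(−0.15) × 1.15 = 0.0102
- d = 4: 1 − exp(−0.20) × 1.20 = 0.0175
- ratio 1.72

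| r per day | P(3) | P(4) | Ratio | Expected in 30 active, dose 1 vs dose 2 | Excess |
|---|---|---|---|---|---|
| 0.01 | 0.044% | 0.078% | 1.77 | 0.01 vs 0.02 | 0.01 |
| 0.05 | 1.02% | 1.75% | 1.72 | 0.31 vs 0.53 | 0.22 |
| 0.10 | 3.7% | 6.2% | 1.67 | 1.11 vs 1.85 | 0.74 |
| 0.20 | 12.2% | 19.1% | 1.57 | 3.66 vs 5.74 | 2.08 |

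The low-rate limit is (4/3)² = 1.78. If dosing at midday makes the windows 2.5 and 3.5 days, the ratio is 1.73 to 1.95.

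With 30 active participants and the two doses treated as independent, chance alone gives more PCREs after dose 2 than after dose 1 with probability 33% at r = 0.05 (fewer 17%, tie 51%) and 71% at r = 0.20 (fewer 18%).

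**Reading 2: rows by dose level.** A Part B participant can be flagged in either window (3 + 4 = 7 days), a Part A participant in one (3 days). The ratio is [1 − (1 − P(3))(1 − P(4))] / P(3):
- r = 0.01: 2.77
- r = 0.05: 2.70
- r = 0.10: 2.60
- r = 0.20: 2.38

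Part of this comes from having two administrations. With 3 days after each dose the ratio would still be [1 − (1 − P(3))²] / P(3) = 2 − P(3), that is 1.99 at r = 0.05 and 1.88 at r = 0.20. Equal windows alone do not remove it; counting per administration does.

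**What would cancel the excess.** If the recorded rate after dose 2 were 25% lower, then 0.75 × 4 = 3 and the ratio returns to 1.00.

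**After the change.** With equal windows and per-administration counts the ratio is 1.00 at any r, given equal rates and recording.

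**The case against.** A reader might infer that the unequal windows make the second dose look worse. The documents do not support that as a settled result, for four reasons.

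- **The link is not stated.** The windows are attached to the listings, while the PCRE has its own undefined short window. Elsewhere the SAP usually uses dose to mean dose level, and on that reading there is no dose 2 row. This stands. It changes which comparison is distorted, not whether one is, because search time is unequal on both readings.
- **The direction is open.** After dose 1 there is an inpatient stay to Day 2, assessment to 12 hours and a Day 4 clinic visit. After dose 2, scheduled assessments end at 8 hours, Day 30 is a phone visit and the next scheduled visit is Day 36 (Protocol, Schedule of Activities). Participants who meet an individual stopping rule receive no second dose (Protocol 3.4.3). Both features push dose 2 counts down. This stands, but the SAP does not offer it as the reason for the extra day, and one inequality does not correct another by a known amount.
- **The numbers are small.** Rates of 0.05 to 0.20 per day imply about 6 to 22 listed events per participant over 112 days (0.05 × 112 = 5.6; 0.20 × 112 = 22.4), which may be high. At 0.01 per day the excess is about 0.01 of 30 participants. This stands and limits the importance of the point.
- **Placebo shares the windows.** Within Part B, active against placebo after the same dose is not biased by window length. SAP 8.3 splits safety summaries by treatment, which partly covers this, although the PCRE table is not itself said to show placebo.

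A reader might also infer that the windows or the open term list were fitted to unblinded data. The documents show a sponsor-open design and an analysis declared exploratory; they do not show that.

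**Conclusion.** The point holds as a limited one. SAP 8.3.4 gives unequal search windows without a reason, and no other window is available to define a PCRE. If they do define it, chance PCREs are about 1.6 to 1.8 times as likely after dose 2 as after dose 1. By dose level, they are about 2.4 to 2.8 times as likely for a Part B participant as for a Part A participant.

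These ratios rest on constant, independent background events and on equal rates and recording after both doses. They vary little with the assumed rate. The absolute excess does vary with it: about 0.2 to 2 of 30 active participants at 0.05 to 0.20 terms per day, and close to nothing at 0.01. Since observation is lighter after dose 2, the net direction cannot be fixed from the documents. The windows can distort the comparison; they do not certainly count against dose 2. This is a minor but easily corrected flaw in a supporting safety table.

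**What to change.** In SAP 8.3.4, state one PCRE window of the same length after each dose. Two versions would serve: Day 1 to 4 after both doses, so that no event now listed is dropped, or Day 1 to 3 after both, with Day 4 as a sensitivity table. Tabulate PCREs per administration within dose level, with the number dosed at that administration as denominator and placebo alongside. If the fourth day after dose 2 is wanted because observation is lighter then, say so and show the equal-window table as well.

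The cost is SAP wording and at most one extra table. The downside is that a few Day 4 events move into or out of the main table. The change does not equalise the intensity of observation after the two doses, so the table needs a footnote on the lighter schedule after Day 29.

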7.1.12. Infusion Site Reactions

Subjects will be continuously monitored for infusion site reactions from the start of drug administration until the end of infusion and then at time points indicated in the [Schedule of Activities](#). Infusion site reactions may be monitored beyond the time points indicated in the [Schedule of Activities](#) based on investigator's assessment.

Infusion reactions may include but are not limited to: rash, flushing, hypotension, tachycardia, throat irritation or discomfort, difficulty swallowing, fever, chills. Any signs or symptoms related to either an infusion or injection site reaction(s) should be treated according to the investigator's standard of care and reported as adverse events. See [Appendix 7](#) for details regarding the grading of adverse events arising from infusion reactions. Infusion reactions will be categorized according to the following definitions:

1. **Acute:** From start of infusion to 2 hours after the infusion. Infusion reaction AEs that occur during this time period be further classified as follows:
 - a. **Serious:** Infusion reactions that meet the criteria of an SAE.
 - b. **Dose interrupted:** Associated with temporary or permanent interruption and/or modification in dose.
 - c. Infusion reaction AEs based on investigator's judgment.
2. **Immediate:** 2 hours after the infusion to 24 hours after initiation of treatment. Infusion reaction AEs that occur during this time period can be further classified as follows:
 - a. **Serious:** Infusion reactions that meet the criteria of an SAE.
 - b. Infusion reaction AEs based on investigator's judgment.
3. **Late (delayed):** 2 days to 14 days after initiation of treatment:
 - a. **Serious:** Infusion reactions that meet the criteria of an SAE.
 - b. Infusion reaction AEs based on investigator's judgment.

Information regarding infusion reactions will be collected on the Adverse Event Record. If the infusion reaction requires a modification to the administration of test article, the information must be recorded on the Test Article Record. All infusion reactions that are considered SAEs should be reported as specified in [Section 8.2.3](#).

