Cytokine release syndrome/acute infusion reaction	Cytokine release	Mild reaction; infusion interruption not indicated; intervention not indicated	Requires therapy or infusion interruption but responds promptly to symptomatic treatment (eg, antihistamines, NSAIDS, narcotics, IV fluids); prophylactic medications indicated for ≤ 24 hrs	Prolonged (ie, not rapidly responsive to symptomatic medication and/or brief interruption of infusion); recurrence of symptoms following initial improvement; hospitalization indicated for other clinical sequelae (eg, renal impairment, pulmonary infiltrates)	Life-threatening; pressor or ventilatory support indicated	Death

Remark: Cytokine release syndromes/acute infusion reactions are different from Allergic/hypersensitive reactions, although some of the manifestations are common to both AEs. An acute infusion reaction may occur with an agent that causes cytokine release (eg, monoclonal antibodies or other biological agents). Signs and symptoms usually develop during or shortly after drug infusion and generally resolve completely within 24 hrs of completion of infusion. Signs/symptoms may include: Allergic reaction/hypersensitivity (including drug fever); Arthralgia (joint pain); Bronchospasm; Cough; Dizziness; Dyspnea (shortness of breath); Fatigue (asthenia, lethargy, malaise); Headache; Hypertension; Hypotension; Myalgia (muscle pain); Nausea; Pruritis/itching; Rash/desquamation; Rigors/chills; Sweating (diaphoresis); Tachycardia; Tumor pain (onset or exacerbation of tumor pain due to treatment); Urticaria (hives, welts, wheals); Vomiting.

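### The cytokine-release count in SAP 8.3.4 needs two symptom terms, so a reaction recorded only as cytokine release syndrome is missing from that table and its listing

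*SAP*

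**What the plan says.** SAP 8.3.4 (Adverse Events) sets out a search for possible cytokine release syndrome.

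- **Terms.** "The set of preferred term of interest will include tachycardia, hypotension, hypertension, chills, vomiting, nausea, headache, pyrexia, dizziness, and palpitations". All ten are single signs or symptoms.
- **Counting rule.** "The observation of a group of two or more events from this set within a short time window after the dosing" is treated as a potential event, abbreviated PCRE.
- **Window.** The companion listings take participants with a term of interest starting on Days 1 to 3 after the first dose or Days 1 to 4 after the second. The counting rule itself gives no days.
- **Output.** A tabulation of total participants and "number and percent of PCREs within each of the doses will be created".
- **Status.** "Note that this analysis is exploratory and the list of preferred terms may be modified if needed".

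The same section plans separate listings of infusion-related reactions and injection site reactions. On grading it says: "In the case report forms (CRF) the infusion-related adverse effect was characterized by toxicity grade".

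In the protocol, Appendix 7 grades "Cytokine release syndrome/acute infusion reaction" as one adverse event row. Section 7.1.12 says: "Information regarding infusion reactions will be collected on the Adverse Event Record". That section also asks for signs and symptoms of a reaction to be reported as adverse events. It does not say whether the diagnosis, its components or both should be entered.

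**The concern.** The rule looks for the syndrome through its symptoms and has no route for the syndrome itself. The clearest possible record, an investigator's diagnosis of cytokine release syndrome, scores zero when it stands alone. Two mild, non-specific symptoms score one. The by-dose count therefore depends partly on how a site words its adverse events.

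Safety and tolerability is the primary objective. Protocol 1.2.6 reports cytokine release in human cells in vitro, although none was detected in the monkey toxicity studies. The PCRE table is the only count in the readable SAP text aimed specifically at this risk by dose. With three or six active participants per cohort, one record can change how a dose level looks.

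**Working it through.** The plan attaches no figure to this analysis, so there is none to reproduce. The check applies the rule as written and then shows what one uncounted record is worth.

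**Step 1: apply the rule.** A participant is a PCRE if at least two recorded events carry one of the ten terms. The listing needs at least one such term. All example events are taken to fall inside the window.

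| Adverse events recorded | Listed terms | PCRE? | In companion listing? |
|---|---|---|---|
| cytokine release syndrome | 0 | no | no |
| infusion related reaction | 0 | no | no |
| infusion related reaction, pyrexia | 1 | no | yes |
| pyrexia, chills | 2 | yes | yes |
| nausea, headache | 2 | yes | yes |

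**Step 2: test the modification clause.** The clause lets the term list change. If cytokine release syndrome were added, a lone diagnosis would give one listed term. That would bring it into the listing, but 1 < 2, so it would still fail the count. The table needs a change to the rule as well as to the list.

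**Step 3: weight of one record.** SAP Table 1 expects 3 active participants in each of A1 to A4 and 6 in each of A5, A6 and B1 to B5.

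- 1/6 = 16.7 percentage points
- 1/3 = 33.3 percentage points

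**Step 4: illustration with assumed rates.** Neither input below is in the documents. Let p be the true reaction rate and q the share of reactions recorded as the diagnosis alone, without two listed symptoms. Assume every other reaction meets the symptom rule. For n = 6 and p = 1/3, the expected count is n·p·(1 − q), and the chance of at least one counted event is 1 − [1 − p(1 − q)]^6.

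| q (assumed) | Expected true | Expected counted | Chance of at least one counted |
|---|---|---|---|
| 0% | 2.0 | 2.0 | 1 − (2/3)^6 = 91.2% |
| 25% | 2.0 | 1.5 | 1 − (3/4)^6 = 82.2% |
| 50% | 2.0 | 1.0 | 1 − (5/6)^6 = 66.5% |
| 100% | 2.0 | 0 | 0% |

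If a diagnosis could qualify alone, all rows would stand at 2.0 and 91.2%. The table shows sensitivity to recording style. It does not estimate what happened in this trial.

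**The case against.** Most of the case on the other side concerns consequences, and much of it is right.

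**Other outputs show the event.** A reader might infer that a diagnosed reaction disappears from the safety report, or that nothing else tabulates it. The documents do not support that. SAP 8.3 plans summary tables by treatment, and 8.3.4 keeps the standard adverse event summaries, in which the coded diagnosis would appear. An infusion-related case would also be in the infusion-reaction listing. After SC dosing this is less clear, because the injection site features in Protocol 7.1.13 are local. SAP Table 1 shows B1 to B5 as SC, which is 5 × 6 = 30 of the 54 expected active participants in the cohorts used (4 × 3 + 2 × 6 + 30 = 54).

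**Purpose.** The search can be read as a screen for cases that sites did not label, and the SAP calls it exploratory. No hypothesis or decision rule uses it. That lowers the stakes. It does not explain why a labelled case should be absent from a table of possible cases.

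**Recording practice.** Protocol 7.1.12 points partly towards reporting symptoms, and Appendix 7 also has separate rows for hypertension, hypotension, fever and chills. The SAP remark on toxicity grades fits graded individual symptoms as well as a graded diagnosis. Nothing shows that any reaction was recorded as a diagnosis alone. This objection stands, and it is why no rate of loss can be stated.

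**Symptom list.** A reader might also fault the ten terms for covering only part of the signs in the Appendix 7 remark. That is not a sound criticism. Appendix 7 is a grading table, its drug fever overlaps with pyrexia, and the remark itself separates these reactions from allergic ones. Which symptoms to search is a matter of judgement.

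**Conclusion.** The point holds, within limits. As written, a reaction recorded solely as cytokine release syndrome contributes nothing to the by-dose PCRE table or to its listing, and the freedom to edit the term list does not cure the table. This follows from the SAP text without any assumption.

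Its practical size is conditional. Each such record removes 16.7 points in a six-active cohort or 33.3 in a three-active one, but only if the participant does not also have two listed symptoms recorded. The number of such records could be none. The gap affects one exploratory signal table, and the standard adverse event summaries are unaffected. It is worth correcting because the correction is small.

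**What to change.** In SAP 8.3.4, state that any adverse event coded to cytokine release syndrome within the search window qualifies as a PCRE on its own and brings the participant into the listing. Give the listing's day ranges as the window for the count too. Tabulate by dose, in separate rows:

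- (a) participants with a cytokine release syndrome diagnosis;
- (b) participants with two or more of the listed symptom terms, as now;
- (c) participants with an infusion related reaction or systemic injection reaction recorded as a single term, not pooled into the PCRE count.

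If a PCRE total is shown, it should be participants with (a) or (b), each counted once.

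The cost is a short SAP insertion and minor programming on data already collected. The stated PCRE rate may rise slightly. Row (c) may include reactions that are not cytokine release, which is why it stays separate. The study is sponsor-open and the SAP already records the doses used, so the added rows should be labelled exploratory. Row (b) should stay unchanged so that the effect of the new rule is visible.

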8.3.5. Laboratory Data

Laboratory data will be listed and summarized by treatment in accordance with the sponsor reporting standards. Baseline is as defined in [Section 6.2.2](#).

8.3.6. Vital Signs Data

Absolute values and changes from baseline for systolic and diastolic blood pressure and pulse rate will be summarized by treatment group and time post-dose, according to sponsor reporting standards. Tables will be paged by parameter. Baseline is as defined in [Section 6.2.3](#).

Mean changes from baseline for systolic and diastolic blood pressure and pulse rate will be plotted against time post-dose. On each plot there will be 1 line for each treatment. Data from all cohorts will be plotted on the same figure using separate lines for the 2 placebos. Corresponding individual plots of changes from baseline will also be produced for each treatment group.

For systolic and diastolic blood pressure and pulse rate, the differences between each dose and placebo (dose – placebo) will be summarized (N, mean, 90% confidence interval) and plotted (mean) for each treatment group, dose and time point (including baseline).

Maximum absolute values and changes from baseline for vital signs will also be summarized descriptively by treatment using categories as defined in [Appendix 1](#). Numbers and percentages of participants meeting the categorical criteria will be provided. All planned and unplanned post dose time points will be counted in these categorical summaries. All values meeting the criteria of potential clinical concern will be listed.

If necessary, maximum increases or decreases in vital signs may be summarized in addition to the above.

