8.3.7. ECG Data

Absolute values and changes from baseline in QT, heart rate, QTcF, PR and QRS will be summarized by treatment group, and time postdose using sponsor reporting standards. Tables will be paged by parameter. Baseline is as defined in [Section 6.2.4](#).

Mean changes from baseline in QT, heart rate and QTcF will be plotted against time postdose. On each plot there will be 1 line for each treatment. Data from all cohorts will be plotted on the same figure using separate lines for the 2 placebos. Corresponding individual plots of changes from baseline will also be produced for each treatment group.

Changes from baseline in QTcF will also be plotted separately against drug concentrations. This will be a scatter plot for all observations where QTcF and drug concentration are recorded. Placebo data will also be included (with drug concentration set to zero). Different symbols will be used for each treatment. There will be 1 plot for each cohort.

Maximum increase from baseline (0 to 12 hours) for QTcF, heart rate, QT, PR and QRS will be summarized by treatment group, according to sponsor reporting standards.

In addition for QTcF, heart rate and QT, the differences between each dose and placebo (dose – placebo) for each subject will be summarized and plotted (N, mean, 90% confidence interval) for each cohort, dose and timepoint (including baseline).

ECG endpoints and changes from baseline (QTcF, PR and QRS) will also be summarized descriptively by treatment group using categories as defined in Appendix 1 (for QTc these correspond to ICH E14¹). Numbers and percentages of participants meeting the categorical criteria will be provided. All planned and unplanned post-dose timepoints will be counted in these categorical summaries. All values meeting the criteria of potential clinical concern will be listed.

Listings of participants with any single post-dose value ≥ 500 msec will also be produced for QTcF.

QTcB will be listed only and not summarized.

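### The dose-minus-placebo differences in vital signs and ECG appear to be planned on raw values with no baseline adjustment; one ANCOVA per part on the Day 1 baseline would be more precise unless the baseline correlation is low

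*SAP*

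**What the plan says.** For systolic and diastolic blood pressure and pulse rate, SAP 8.3.6 says that the difference between each dose and placebo is to be summarised with N, mean and a 90% confidence interval, and "plotted (mean) for each treatment group, dose and time point (including baseline"). For QTcF, heart rate and QT, SAP 8.3.7 says that the difference "for each subject will be summarized and plotted (N, mean, 90% confidence interval) for each cohort, dose and timepoint (including baseline"). Neither sentence says whether the difference is taken on observed values or on changes from baseline. Neither says which placebo subjects form the comparator.

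Baseline is defined: SAP 6.2.3 takes the last Day 1 pre-dose value for vital signs, and SAP 6.2.4 takes the mean of the Day 1 pre-dose triplicate for ECG. SAP 6.7 (Covariates) contains only the entry None.

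The same two sections use baseline elsewhere. For vital signs, "Absolute values and changes from baseline for systolic and diastolic blood pressure and pulse rate will be summarized by treatment group" and time, and "Mean changes from baseline for systolic and diastolic blood pressure and pulse rate will be plotted against time post-dose". For ECG, "Mean changes from baseline in QT, heart rate and QTcF will be plotted against time postdose". The plots put all cohorts on one figure, "using separate lines for the 2 placebos". These displays are by treatment group. No placebo-corrected change, and no interval for one, is stated.

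**The concern.** Changes in vital signs and ECG are among the primary endpoints (Protocol section 2). In the SAP text available, these contrasts are the only between-group estimates with intervals for them. Two features of the wording suggest that baseline is left out. First, a change from baseline is zero at baseline in every subject, so a dose-minus-placebo difference shown at baseline is informative only on raw values. Second, where the SAP means change from baseline in these sections, it says so.

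Baseline levels can differ by chance. Dose groups have 3 or 6 active subjects (SAP Table 1), ages run from 18 to 70 and BMI from 17.5 to 40 (Protocol 4.1), and no minimum number of SLE or RA subjects is set per cohort (Protocol 4.3). One baseline gap then feeds into every post-dose difference for that dose. Repeated over many time points, it can look like a consistent effect or mask one. The per-subject wording in 8.3.7 adds to the doubt: in a parallel-group trial no subject receives both dose and placebo, so that difference is undefined.

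**Working it through.** **Plan figures.** The documents give no SD, correlation or precision target for these contrasts; Protocol 9.1 says that the sample size has no statistical basis. The only total to check is enrolment: 4×4 + 4×8 + 5×8 + 24 = 112, which agrees with SAP Table 1.

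**Inputs from SAP Table 1 (cohorts used, planned sizes).**
- A1–A4: 3 active and 1 placebo each. A5–A6 and B1–B5: 6 active and 2 placebo each.
- Placebo pooled within part: A = 4×1 + 2×2 = 8; B = 5×2 = 10. Pooling is an assumption. The SAP mentions two placebo groups only for plots.

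**Assumptions.** Equal SD at baseline and post-dose; rho from 0.3 to 0.9; for illustration, SD 16 ms for QTcF and 14 mmHg for systolic pressure.

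**1. Chance baseline gap.** SE = SD × √(1/n₁ + 1/n₀).
- 3 vs 8: 0.677 SD = 10.8 ms or 9.5 mmHg
- 6 vs 8: 0.540 SD = 8.6 ms or 7.6 mmHg
- 6 vs 10: 0.516 SD = 8.3 ms or 7.2 mmHg

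**2. Carry-over.** Given a baseline gap g, the expected post-dose gap with no drug effect is rho × g. The share of the raw contrast's variance due to baseline is rho²: 9%, 25%, 49%, 64% and 81% at rho 0.3, 0.5, 0.7, 0.8 and 0.9. It passes one half only above rho = √0.5 ≈ 0.71, and group size does not enter.

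**3. Raw 90% half-width.** t(0.95, n₁+n₀−2) × SE. For 6 vs 8: 1.782 × 0.540 = 0.96 SD, or 15.4 ms for QTcF. For 3 vs 8 it is 1.24 SD, and for 6 vs 10 it is 0.91 SD. Read within cohort, it is 3.37 SD (3 vs 1) or 1.59 SD (6 vs 2).

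**4. Effect of adjustment, 6 vs 8.** Multiply the SE by √(1−rho²), use one fewer degree of freedom (t = 1.796 on 11), and multiply by √(1+1/11) for estimating the slope. The change-score ratio is √(2(1−rho)).

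| rho | ANCOVA / raw | QTcF half-width, ANCOVA | change score / raw |
|---|---|---|---|
| 0.3 | 1.00 | 15.5 ms | 1.18 |
| 0.5 | 0.91 | 14.0 ms | 1.00 |
| 0.7 | 0.75 | 11.6 ms | 0.77 |
| 0.8 | 0.63 | 9.7 ms | 0.63 |

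The ANCOVA gain is 9%, 25% or 37% at rho 0.5, 0.7 or 0.8. For 3 vs 8 the ratios are 1.03, 0.93, 0.77 and 0.65 in the same row order.

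**5. Residual degrees of freedom with one model per part.** Part A: 32 subjects − 7 groups − 1 slope = 24. Part B: 40 − 6 − 1 = 33. Pooling the variance within part therefore costs little even for the 3-subject doses.

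**6. Validity of the raw interval.** In simulation (100,000 trials per setting) the raw contrast was unbiased and its 90% interval covered 0.899 to 0.903. Among trials whose baseline gap exceeded 1 SE, coverage fell to about 0.84–0.87 at rho 0.5 and 0.75–0.81 at rho 0.8.

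**The case against.** The case for leaving the plan alone has real substance.

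- These are descriptive summaries: SAP 4.1, 4.2 and 8.1 exclude hypotheses, decision rules and formal testing. **Stands**, and it limits importance.
- Change from baseline is already summarised and plotted by treatment with placebo on the same figure, categorical changes are tabulated, and the contrast is itself shown at baseline, so an imbalance would be visible. **Stands**, but the reader would have to do the correction by eye, without an interval.
- The raw scale is an inference. **Stands.** If the inference is wrong, the sentence still needs to name its scale.
- Pooling of placebo is not stated for these contrasts, and 8.3.7 asks for them "for each cohort, dose and timepoint (including baseline"). Within a 3 vs 1 cohort, an ANCOVA would have 1 residual degree of freedom. **Stands** against a model per cohort, not against one per part.

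A reader might also infer that chance imbalance dominates the estimate, that small groups are the reason, that the gap passes unchanged into every time point, or that the interval is invalid. The documents support none of these. Dominance needs rho above about 0.71, and no rho is given. Small groups enlarge the gap and the interval but not baseline's share of the variance. The expected carry-over is rho times the gap, unchanged only at rho = 1. Average coverage is nominal; the shortfall is conditional on an observed imbalance.

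**Conclusion.** The point holds in a moderate form. As worded, the SAP's dose-minus-placebo contrasts appear to be raw, no baseline adjustment is planned, and no placebo-corrected, baseline-adjusted estimate with an interval is described. The cost is mainly precision, plus intervals that mislead when a sizeable baseline gap happens to occur. The gain from adjustment depends on a correlation that the documents do not give, and it vanishes near rho 0.3. The percentages assume equal SDs and placebo pooled within part; they do not depend on the illustrative 16 ms and 14 mmHg. The undefined comparator and the per-subject phrase need correcting whatever rho is. The change is worth making because it is cheap, but it is not a threat to the trial's conclusions.

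**What to change.** In SAP 8.3.6 and 8.3.7:

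1. Report the dose-minus-placebo difference and 90% confidence interval at each post-dose time from one ANCOVA per part, with all doses plus that part's pooled placebo, of the post-dose value on treatment and the Day 1 baseline of 6.2.3 or 6.2.4.
2. State that placebo is pooled within part.
3. Delete the per-subject wording in 8.3.7.
4. Keep the raw baseline difference as a separate descriptive row.
5. Amend 6.7 to list Day 1 baseline as the covariate for these contrasts.

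A simple difference of mean changes is not a good substitute: it is about 18% wider than raw at rho 0.3, no better at 0.5, and gains only above that.

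The cost is SAP wording, minor programming and one degree of freedom per model. The model also assumes a common slope and residual variance across the doses within a part, which the SAP should state. No new data are needed.
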